NON-INTERVENTIONAL (NI) STUDY PROTOCOL

Study information

Title	Safety and effectiveness of LORLAtinib as a FIRST-line treatment in an ALK-positive Advanced Non-Small Cell Lung Cancer Spanish population. (LORLA-FIRST).		
Protocol number	B7461054		
Protocol version identifier	Version 1.0		
Date	10 April 2025		
EU Post Authorization Study (PAS) register number	EUPAS1000000406		
Active substance	Lorlatinib (L01ED05)		
Medicinal product	Lorlatinib		
Research question and objectives	What is the spectrum of adverse events and mitigation strategies associated with lorlatinib as a first line treatment in an ALK+ NSCLC real-world Spanish population? Primary Objective		
	To describe all the spectrum of the adverse events (AEs) of Lorlatinib (CTCAE v6) and its mitigation strategies, with special interest in CNS AEs		
	Secondary Objectives		
	To identify factors that are predictive of AEs, with special interest in CNS AEs		
	To evaluate the effectiveness of 1L lorlatinib in real-world practice		
	rwPFS rate at 12 and 18 months in the ITT population with and without brain metastasis at baseline		

	2. rwDuration of Response (DoR)					
	 rwDuration of Treatment (DoT) rwTime to next therapy/treatment (TTNT) rwSystemic and intracranial Objective Response rate (ORR) using Response Evaluation Criteria in Solid Tumors (RECIST v1.1.) criteria rwTime to intracranial progression rate at 12 and 18 months with and without brain metastasis at baseline rwCumulative incidence of brain metastases (BM) in ITT population at 12 and 18 months (with and without baseline BM) rwOverall survival (OS) rate at 12 and 18m To evaluate the impact of lorlatinib on patients' quality of life 					
	4. rwTime to next therapy/treatment (TTNT)					
	using Response Evaluation Criteria in Solid Tumors (RECIST					
	population at 12 and 18 months (with and without baseline					
	8. rwOverall survival (OS) rate at 12 and 18m					
	To evaluate the impact of lorlatinib on patients' quality of life					
	To describe ALK testing methods used					
	Exploratory Objectives (up to 30 patients)					
	To identify neuroimaging markers (Magnetic Resonance Imaging; MRI) that are predictive of the occurrence of CNS AEs					
Country(ies) of study	Spain					
Author	[name]					
	MAS Sr Team Lead					

2. LIST OF ABBREVIATIONS

Abbreviation	Definition
AE	Adverse Event
ALCL	Anaplastic large cell lymphoma
ALK	Anaplastic Lymphoma Kinase
BM	Brain metastases
CNS	Central Nervous System
CR	Complete Response
CRF	Case Report Form
CTCAE v.6	Common Terminology Criteria for Adverse Events Version 6
ctDNA	Circulating tumour DNA
DOR	Duration of Response
DOT	Duration of the Treatment
DP	Disease Progression
eCRF	Electronic Case Report Form
ECOG	Eastern Cooperative Oncology Group
EORTC QLQ C30	European Organization for Research and Treatment of Cancer,
	Quality of Life Questionnaire C30
FISH	Fluorescent in situ hybridization
HR	Hazard Ratio
ICO	Catalonian Institute of Oncology
IHC	Immunohistochemistry
ITT	Intention-to-treat
IEC	Independent Ethics Committee
MRI	Magnetic Resonance Imaging
NGS	Next Generation Sequencing
NIS	Non-Interventional Study
NSCLC	Non-Small Cell Lung Cancer
NR	Not reached
ORR	Objective Response Rate
OS	Overall Survival
PASS	Post-Authorisation Safety Study
PFS	Progression-Free Survival
PR	Partial Response
PRO-CTCAE	Patient Reported Outcomes version of the common terminology
	criteria for Adverse events
QoL	Quality of life
RECIST v1.1	Response Evaluation Criteria in Solid Tumors
Rw	Real-World
rwPFS	Real world Progression Free Survival
SAE	Serious Adverse Event
SD	Stable Disease

TKI	Tyrosine-kinase inhibitor
TMB	Tumoral Mutational Burden
TTNT	Time to next therapy/treatment

Anaplastic lymphoma kinase (ALK) rearrangements occurred in 3-5% of lung adenocarcinomas¹. ALK rearrangements stimulate tumor growth and disease progression. During the last decade, multiple ALK inhibitors were developed and demonstrated significant improvement in the clinical outcomes for patients with ALK-positive non-small cell lung cancer (NSCLC). Lorlatinib, a third generation ALK inhibitor, has shown greater potential as a first-line therapy based on the results of the CROWN trial. This was a randomized open-label phase III trial comparing lorlatinib with crizotinib, a first-generation ALK inhibitor, in 296 treatment-naïve patients with advanced ALK-positive NSCLC. With 5yr of follow up, lorlatinib significantly prolonged progression-free survival (PFS) (median PFS not reached 95% CI (64.3 – NR) for Iorlatinib arm, and 9.1 months for crizotinib arm (95% CI 7.4 – 10.9), hazard ratio (HR) 0.19 with 95%CI (0.13 - 0.27) by investigator assessment), increased response rates, and enhanced central nervous system (CNS) efficacy compared to crizotinib. In the pivotal phase I/II study, with a median follow-up for OS of 72.7 months (95% CI, 69.3 to 76.3), median OS was NR (95% CI, NR to NR) with lorlatinib, and 5-year OS was 76% (95% CI, 57 to 88) in patients with treatment-naïve ALK-positive NSCLC (n=30)² Lorlatinib also had a manageable safety profile consisting of hyperlipidemia, weight gain, and hypertension being the most common G3/4 adverse events³. Lorlatinib was associated with adverse events involving the CNS and causing mood/speech and cognitive alterations that generate some uncertainties regarding an adequate management⁴. AT 3yr of follow up of the CROWN study, cognitive functioning scores slightly declined over time in patients with or without CNS AEs, however, this was not clinically significant. Emotional functioning scores generally improved over time, independent of presence or absence of CNS AEs. CNS AEs with lorlatinib were mostly grade 1 or 2 and more than half of all CNS AEs resolved without intervention or with lorlatinib dose interruption⁵.

Based on the utilization of lorlatinib in patients who received previous ALK inhibitors, several factors have associated with higher risk of CNS adverse event (AE) such as prior brain

radiotherapy, presence/absence of baseline intracranial metastasis, use of concomitant drugs, or personal clinical history of psychiatric/mood diseases⁶. However, limited data are available about the occurrence of CNS AEs when lorlatinib is used in the first line of treatment (local approval in Spain February 2023) in a real-world population.

On the other hand, lorlatinib has proved its efficacy and safety in clinical trials, but real-world evidence is needed to confirm these results in wider patient populations and to identify prognostic and predictive factors not captured in clinical trials. Ethnicity, molecular variants, and circulating tumour DNA (ctDNA) clearance may influence treatment outcomes and require personalized or combinational approaches.

Research question and objectives

Research question

 What is the spectrum of adverse events and mitigation strategies associated with lorlatinib as a first line treatment in an ALK+ NSCLC real-world Spanish population?

Primary Objective

 To describe all the spectrum of the adverse events (AEs) of Lorlatinib (CTCAE v6.0) and its mitigation strategies, with special interest in CNS AEs

Secondary Objectives

- To identify factors that are predictive of AEs, with special interest in CNS AEs
- To evaluate the effectiveness of 1L lorlatinib in real-world practice
 - 1. rwPFS rate at 12 and 18 months in the ITT population with and without brain metastasis at baseline
 - 2. rwDuration of Response (DoR)
 - 3. rwDuration of Treatment (DoT)
 - 4. rwTime to next therapy/treatment (TTNT)
 - 5. rwSystemic and intracranial Objective Response rate (ORR) using Response Evaluation Criteria in Solid Tumors (RECIST) v1.1. criteria
 - 6. rwTime to intracranial progression rate at 12 and 18 months with and without brain metastasis at baseline
 - 7. rwCumulative incidence of brain metastases (BM) in ITT population at 12 and 18 months (with and without baseline BM)

- 8. rwOverall survival (OS) rate at 12 and 18m
- To evaluate the impact of lorlatinib on patients' quality of life
- To describe ALK testing methods used

Exploratory Objectives (up to 30 patients)

 To identify neuroimaging markers (Magnetic Resonance Imaging; MRI) that are predictive of the occurrence of CNS AEs

Study Design

The study is an observational, non-interventional, prospective and multicenter trial that evaluates the real-world safety and effectiveness of lorlatinib as a first-line treatment in patients with ALK-positive advanced NSCLC in Spain.

Additionally, our study population exhibits a low incidence of NSCLC patients, approximately 3-4%. Consequently, the current study is descriptive in nature.

Study Population

Patients in 20 Spanish hospitals (clinics, or and primary care centers) must have a confirmed diagnosis of locally advanced and/or metastatic NSCLC with an ALK rearrangement identified by an approved diagnostic test, be older or equal than 18 years and have initiated first-line therapy with lorlatinib at least 7 days and up to 28 days prior to enrolment in the study according to routine clinical practice. They must also sign an informed consent and have a minimum of predetermined data recorded in their medical records. Socio demographic data about the patient's gender, age, height, weight at the treatment initiation will be collected. Additional socio demographic data will be collected: race, along with details regarding their smoking habits, as well as exposure to asbestos and previous personal and family history of cancer, particularly in first-degree relatives. Patients included in clinical trials are also excluded.

Study variables

The following variables will be collected: AE, serious adverse events (SAE), and scenarios involving: exposure during breast feeding, medication error, overdose, misuse, extravasation, lack of efficacy; exposure during pregnancy (EDP), occupational/environmental exposure and treatment-associated mortality as well as time to onset and duration of AEs. Likewise, effectiveness variables as rwPFS rate at 12 and 18 months in the ITT population with and without brain; metastasis at baseline, rwDuration of Response (DoR); rwDuration of Treatment (DoT), rwTime to next therapy/treatment (TTNT)M; rwSystemic and intracranial Objective Response rate (ORR) using Response Evaluation Criteria in Solid Tumors (RECIST v1.1). criteria, rwTime to intracranial progression rate at 12 and 18 months with and without brain metastasis at baseline, rwCumulative incidence of brain metastases (BM) in ITT population at 12 and 18 months (with and without baseline BM), rwOverall survival (OS) rate at 12 and 18m.

Sociodemographic, clinical variables prior to start treatment/on treatment/after treatment with lorlatinib and quality of life data of patients under treatment will be collected.

Data sources

The investigators will collect the data of the patients included in an electronic data collection form (e-CRF) designed specifically for this study and developed by the CRO in charge at the beginning of the study. The data will be stored in an access database protected by password and only accessible to authorized personnel. Descriptive and survival analyses will be performed to evaluate the study objectives, using the Kaplan-Meier method and the Cox model. The AEs will be summarized by presenting the frequency distribution and percentage of these in the total number of patients and will be coded according to the CTCAE v6.0.

Imaging data^{9,10}

Brain MRI will be collected at baseline and in case of CNS toxicity. Images will be anonymized and centrally analyzed (See Section 9.3.7) to assess Fazekas scale, morphometric and radiomic features that will be correlated with CNS toxicity.

Baseline CT scan will be collected to determine the body composition. Images will be anonymized and centrally analyzed to assess radiomic features that will be correlated with CNS toxicity. Baseline body CT scan and brain MRI and first tumor assessment will be collected to determine body composition and to compare radiomic characteristics in patients who developed CNS AEs with those who did not.

Study size

In the CROWN trial, the incidence of CNS AEs was 42% and we assumed that the incidence could be higher in the real clinical practice, but it is probably under detected or recorded as most cases are grade 1. We estimated that we need 116 patients treated with lorlatinib in first-line therapy for ALK+ non-small cell lung cancer with an 80% power to detect an incidence of 55% any grade CNS AEs using a 2-sided test.

Data analysis

The safety assessment will be based primarily on the frequency and severity of AE. AEs will be summarized by presenting the number and percentage of these figures in the total number of patients. The absolute and variable frequencies of each AE with respect to the total number of reported AEs will also be presented. Descriptive analyses will be carried out to evaluate the objectives of the study.

Categorical variables will be described by their absolute and relative frequency. Continuous variables will be described with total n, valid n, n unavailable, means, standard deviation, quartiles, minimum and maximum. Survival analysis will be performed using the Kaplan Meier method. A Cox regression model will be carried out to find independent variables associated with overall survival or time until disease progression.

Milestones

• Expected date of approval by the central IEC: 31 May 2025

• Expected date of opening of the first site: 01 June 2025

• Start recruitment: 01 June 2025

• End recruitment: 30 November 2026

• Recruitment period: 18 months

• Expected date for closing of data collection: 30 November 2027

• Interim Analysis after 18m of FUP of first 50 patients included: 30 April 2027

Expected date of final study report: 31 May 2028

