At a median of follow up of 60.2 months⁴ (95% CI, 57.4 to 61.6) in the lorlatinib group and 55.1 months (95% CI, 36.8 to 62.5) in the crizotinib group. The HR for PFS or death with lorlatinib versus crizotinib was 0.19 (95% CI, 0.13 to 0.27). Median PFS was NR (95% CI, 64.3 to NR) with lorlatinib and 9.1 months (95% CI, 7.4 to 10.9) with crizotinib. The 4- and 5-year PFS was 63% and 60% (95% CI, 51 to 68) with lorlatinib, respectively, and 10% and 8% (95% CI, 3 to 14) with crizotinib. Among patients with baseline brain metastases (measurable and/or non-measurable; n = 35 in the lorlatinib group and n = 38 in the crizotinib group), the HR for PFS or death with lorlatinib versus crizotinib was 0.08 (95% CI, 0.04 to 0.19); median PFS was NR (95% CI, 32.9 to NR) with lorlatinib and 6.0 months (95% CI, 3.7 to 7.6) with crizotinib. Five-year PFS was 53% (95% CI, 35 to 68) with lorlatinib and not evaluable with crizotinib as all patients had progression or death or were censored within 2 years. Among patients without baseline brain metastases, the HR for PFS or death with lorlatinib versus crizotinib was 0.24 (95% CI 0.16 to 0.36); median PFS was NR (95% CI, 64.3 to NR) with lorlatinib and 10.8 months (95% CI, 9.0 to 12.8) with crizotinib. Five-year PFS was 63% (95% CI, 52 to 71) with lorlatinib and 10% (95% CI, 5 to 18) with crizotinib.

Regarding the safety profile of the drug, the median treatment duration was 57.0 months (IQR, 13.9-63.3) with lorlatinib and 9.6 months (IQR, 4.7-17.1) with crizotinib. Overall, 49 of 149 patients (33%) treated with lorlatinib and 36 of 142 (25%) treated with crizotinib had at least one dose reduction. The median relative dose intensity was 99% (IQR, 80-100) with lorlatinib and 99% (IQR, 91-100) with crizotinib. All-causality any-grade AEs occurred in all patients in the lorlatinib group and in 140 of 142 patients (99%) in the crizotinib group; grade 3/4 AEs occurred in 77% and 57% of patients, respectively. A higher rate of grade 3/4 AEs from any cause in the lorlatinib group compared to the crizotinib group was mostly due to hypertriglyceridemia (25% v 0%), hypercholesterolemia (21% v 0%), weight gain (23% v 2%), and hypertension (12% v 1) with lorlatinib, 23% of patients had dose reduction, 62% had temporary treatment interruption, and 11% had permanent discontinuation because of AEs from any cause. Treatment-related AEs caused

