- 1. **Baseline visit:** the day on which the patient fulfils the inclusion and exclusion criterion, including signature of the Informed Consent (i.e. the day on which the prospective observation starts) (within cycle 1 if lorlatinib)
- 2. Follow-up visit 1: will be scheduled at month 3 (third cycle of Iorlatinib)
- 3. Follow-up visit 2: will be scheduled at month 6 (sixth cycle of Iorlatinib)
- 4. Follow-up visit 3: Follow-up visit at month 12 (twelfth cycle of lorlatinib)
- 5. Final Visit: end of follow-up (end of data collection expected November 2027)

Data collection overview

Study Visits and Assessments	Baseline			FU3 C12D1	Final Visit
Informed consent	X				
SOCIO DEMOGRAPHIC DATA					
Medical history	X				
Physical examination including Height and weight	X	X	X	X	X

Study Visits and Assessments	Baseline	FU1	FU2	FU3	Final
		C3D1	C6D1	C12D1	Visit
Previous personal and family history of cancer	X				
CLINICAL DATA					
ECOG	X	X	X	X	X
Laboratory: Hematology and Blood chemistry (dyslipemia profile included). According to routine clinical practice	X	X	X	X	X
Comorbidities since Index Date: Charlson Index	X	X	X	X	X
Concomitant treatment(s) including previous history of Thromboembolic Disease	X	Х	X	X	X
Information of baseline tumor diagnosis: date, staging, (TNM),biopsy, PD-L1 expression, other mutations, etc	X				
Information regarding advanced disease: date, staging, metastatic location, CNS metastasis, previous systemic chemotherapy, radiotherapy, etc	X				
Previous systemic chemotherapy (Yes/No)	X				
Assessments CT scan	X				
Assessments brain MRI	X				
LORLATINIB TREATMENT					
Start, Stop and Discontinuation date	X	X	X	X	X
Dose by cycle	X	X	X	X	X
Reason for discontinuation or for dose reduction	X	X	X	X	X
Evaluation of Treatment Response: method (CT scan, MRI, others) and response	х	Х	X	X	X
AFTER LORLATINIB TREATMENT					

Study Visits and Assessments		FU1	FU2	FU3	Final
		C3D1	C6D1	C12D1	Visit
Post-progression treatment: type and palliative care					X
Date of death or last follow-up or last contact					X
QUALITY OF LIVE					
EORTC QLQ C30, LC13	X	X	X	X	X
SAFETY					
PRO-CTCAE	X	X	X	X	X
Adverse Events	X	X	X	X	X

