9.2.1. Inclusion Criteria

Patients must meet all of the following inclusion criteria to be eligible for inclusion in the study:

- Evidence of histologically or cytologically confirmed diagnosis of locally advanced and/or metastatic NSCLC (Stage IV, AJCC v8.0) harboring an ALK rearrangement identified by an approved diagnostic test. (FISH, IHC, RT PCR, Next generation sequencing, NGS)
- 2. Patients aged ≥18 who have initiated first-line therapy with lorlatinib at least 7 days and up to 28 days prior to enrolment in the study according to routine clinical practice.
- 3. ALK+ patients with intracranial and extracranial disease are allowed.
- 4. Patients should have a minimum of 3 months predetermined data recorded in their medical records.
- 5. Informed consent form personally signed and dated stating that the patient (or their legal representative) has been informed of all relevant aspects of the study.
- 6. ECOG performance status 0-2.
- 7. No previous treatment with an ALK TKI (alectinib, brigatinib, ceritinib, crizotinib. Other systemic treatments if previous relapse in early stages are allowed.

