Variable	Role	Data source(s)	Operational definition
Height at treatment initiation	Baseline patient's characteristics	Investigators Patient clinical record/Electronic Health record (EHR)	• Meters
Weight at treatment initiation (and usual weight prior to diagnosis)	Baseline patient's characteristic	Investigators Patient clinical record/Electronic Health record (EHR)	• Kg
Clinical data prior to the	ne start of trea	tment with lorlati	nib
Patient's clinical situation Performance status before the start of treatment lorlatinib by Eastern Cooperative Oncology Group (ECOG)	characteristics	Investigators Patient clinical record/Electronic Health record (EHR)	Baseline autonomy status of the patient by Eastern Cooperative Oncology Group (ECOG)
Baseline Relevant comorbidities (Yes / No) Charlson Comorbidity Index	Baseline patient's characteristics	Investigators Patient clinical record/Electronic Health record (EHR)	 Lack of co-morbidity: 0-1 Low comorbidity: 2 High Comorbidity: >=3
Past personal or family history of psychiatric or neurological conditions	Baseline patient's characteristic	Investigators Patient clinical record/Electronic Health record (EHR)	Yes/No
Relevant concurrent medications:	Baseline patient's characteristics	Investigators Patient clinical record/Electronic Health record (EHR)	 Neurotropic, Psychiatric and mood medication Anticonvulsants Other

Variable	Role	Data source(s)	Operational definition
Previous history of Thromboembolic Disease	Baseline patient's characteristics	Investigators Patient clinical record/Electronic Health record (EHR)	• Yes/No
embolic origin, regardless	characteristic	Investigators Patient clinical record/Electronic Health record (EHR)	Thrombotic/embolic
Events of thrombotic or embolic origin, regardless	characteristic	Investigators Patient clinical record/Electronic Health record (EHR)	Superficial / deep
emlic origin, regardless	Baseline patient's characteristic	Investigators Patient clinical record/Electronic Health record (EHR)	• Yes/No

Variable	Role	Data source(s)	Operational definition
Information of baseline tumor diagnosis Date of first diagnosis. It is considered the first diagnosis as the first record in the confirmatory clinical history of the presence of tumor lesion by biopsy.	patient's characteristics	Investigators Patient clinical record/Electronic Health record (EHR)	Date format

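### No pre-dose lipid value is specified, so a profile taken 7 to 28 days into treatment can be recorded as baseline; the scheduled Baseline weight is also not reconciled with weight at treatment initiation

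*Protocol*

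**What the plan says.** **Timing.** Inclusion criterion 2 (Section 9.2.1) requires that the patient has "initiated first-line therapy with lorlatinib at least 7 days and up to 28 days prior to enrolment in the study". Section 9.2 defines the Baseline visit as "the day on which the patient fulfils the inclusion and exclusion criterion, including signature of the Informed Consent" and places it within cycle 1. The index date in the same section is the start of lorlatinib, and a pre-index period runs from diagnosis to that date.

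**Lipids.** The data collection overview in Section 9.2 has one relevant row, "Laboratory: Hematology and Blood chemistry (dyslipemia profile included). According to routine clinical practice", marked at Baseline, the three follow-up visits and the Final visit. The variable table in Section 9.3 contains no lipid variable, before or during treatment.

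**Weight.** The schedule has "Physical examination including Height and weight" at the same five visits. Section 9.3 separately lists "Weight at treatment initiation (and usual weight prior to diagnosis"), sourced from the clinical record. The abstract (Study Population) also says that "height, weight at the treatment initiation will be collected".

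**Why these variables count.** The abstract and Section 7 name hyperlipidaemia, weight gain and hypertension as the most common grade 3/4 events. Section 7 gives pivotal-trial grade 3/4 rates on lorlatinib of 25% for hypertriglyceridaemia, 21% for hypercholesterolaemia and 23% for weight gain.

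**The concern.** The schedule calls its first column Baseline, but by the protocol's own eligibility rule the patient has then been on treatment for one to four weeks. For lipids no other value is requested. A site that follows the schedule and the variable list can enter an on-treatment lipid profile as the patient's baseline and still comply fully.

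Three uses of the data are exposed. The primary objective describes the spectrum and severity of adverse events, and Section 11 requires a causality judgement for each; a raised lipid value in week 2 or 3 is hard to class as new, worsened or pre-existing without a pre-dose value in the database. Section 9.3 also collects time to onset, which has the same need. The first secondary objective looks for predictors of adverse events, and a lipid value already affected by the drug is not a clean baseline predictor. In addition, Section 9.7 promises a descriptive analysis of every collected variable, so the Baseline lipid column will be tabulated and read as a description of patients before treatment.

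For weight the issue is smaller. Two candidate baselines exist, and the protocol does not say which one is the reference.

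**Working it through.** The protocol computes nothing for this point, so the check is mainly a comparison of sections, with two short calculations for scale.

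**1. Is the Baseline visit after the first dose?** Yes. Enrolment requires treatment that began 7 to 28 days earlier (Section 9.2.1), and the visit is the day on which eligibility is met and consent signed (Section 9.2). A value measured at the visit is therefore taken 7 to 28 days after the first dose.

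**2. Is a pre-dose value requested elsewhere?**

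| Item | Schedule, Section 9.2 | Variable table, Section 9.3 | Pre-dose value named? |
|---|---|---|---|
| Lipid profile | Baseline and four later visits | No entry | No |
| Weight | Baseline and four later visits | At treatment initiation, plus usual weight before diagnosis | Yes, but not linked to the schedule |
| ECOG | Baseline and four later visits | Status before the start of lorlatinib | Yes |

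No proxy for lipids is named in Section 9.3 either. Comorbidity is a Charlson category. The relevant concurrent medications are neurotropic, psychiatric and mood drugs, anticonvulsants, and an unspecified other group.

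**3. How much treatment time precedes the visit?** The protocol places the first follow-up at month 3 and also at day 1 of cycle 3. It does not state the cycle length, so I take both readings.
- Assuming 28-day cycles, cycle 3 day 1 falls 2 × 28 = 56 days after the first dose: 7/56 = 12.5% and 28/56 = 50%.
- Taking month 3 as day 91: 7/91 = 7.7% and 28/91 = 30.8%.

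Between about 8% and 50% of the time from first dose to the first follow-up lipid value lies before the Baseline visit. This is a share of time, not of lipid change.

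**4. How common are the affected events?** The multiplier is the planned 116 patients. That figure is close to what a one-sample test of 42% against 55% gives with 80% power and an assumed two-sided alpha of 0.05: n = [1.960 × √(0.42 × 0.58) + 0.842 × √(0.55 × 0.45)]² / 0.13² = 113.7, or 114. The present point does not depend on it. At the pivotal trial's grade 3/4 rates:
- hypertriglyceridaemia: 116 × 0.25 = 29.0
- hypercholesterolaemia: 116 × 0.21 = 24.4

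One patient may have both. The rates come from a report with a median treatment duration of 57.0 months. In this study data collection ends 12 months after recruitment closes and 30 months after it opens (Section 6), so the real counts may be lower.

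**The case against.** The strongest reply is that the Baseline column is not necessarily a set of day-of-visit measurements. It also holds tumour staging, medical history and prior chemotherapy, all taken from the record, and ECOG in that column is defined in Section 9.3 as the status before lorlatinib. The lipid row is tied to routine practice and requires no blood draw on the visit day. With an index date at the first dose, a pre-index period, use of electronic records (Section 9.1) and the abstract's promise of clinical variables from before treatment, a site could enter a pre-dose lipid value. This stands in part: the protocol permits an on-treatment lipid baseline but does not compel one. It remains that no field, date or rule asks for the pre-dose value. An analysis plan can choose among collected values but cannot recover one that was never requested.

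A second reply is that adverse events are reported from the first dose, and that the Section 11 criteria for calling an abnormal test an adverse event (symptoms, further testing or intervention, a dosing change, added treatment, judgement) do not use the Baseline-visit value. Nor is a change-from-baseline endpoint defined for lipids or weight. All of this is correct. An early lipid event can be captured with its own onset date, and the investigator has the chart. What is weakened is the evidence in the database for attribution and for predictor analysis, not the capture of events as such.

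A reader might also infer that weight gain has no pre-treatment reference and will be under-graded. The documents do not support that. Weight at treatment initiation and usual weight before diagnosis are both named variables, and nothing says that an analyst would ignore them in favour of the visit weight.

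**Conclusion.** The point holds for lipids in a limited form, and for weight only as a matter of reconciliation. No pre-dose lipid value is specified, and the only lipid item starts at a visit 7 to 28 days after the first dose, so an on-treatment value can be recorded as baseline. Weight has a pre-treatment variable, but the protocol does not say how the schedule's Baseline weight relates to it.

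The events concerned are common: about 29 and 24 of 116 patients if the pivotal trial's grade 3/4 rates carry over, which its longer treatment makes uncertain. A reader might want to turn these counts into a number of misclassified or lost cases. The protocol does not support one, because it gives neither the speed of the lipid rise nor the share of patients whose Baseline entry would be a pre-dose value. The pre-existing state is not wholly invisible either, since medical history and concomitant treatments are collected.

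This is a cheap improvement to data collection. It does not undermine the primary objective.

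**What to change.** - **Section 9.3:** add a baseline variable for the lipid profile, defined as the last value on or before the first lorlatinib dose, with its date, taken from the medical record of the pre-index period.
- **Section 9.2, data collection overview:** state that baseline lipids and baseline weight are these pre-dose values, and that lipids and weight measured at the Baseline visit are the first on-treatment values.
- **No pre-dose value:** leave baseline missing and do not fill it with the on-treatment value. The statistical analysis plan can repeat this rule, but the field has to exist in the eCRF first.

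The cost is a few dated eCRF fields completed from records that the study already opens, with no new test and no change to care. The downside is that some patients will have no pre-dose lipid value, so the number with a usable lipid baseline should be reported.
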